# 7. Study Statistics

a. Primary outcome variable

**Primary Outcome Variable**: The primary outcome variable for this study is change in albuminuria.

b. Secondary outcome variables.

**Secondary Outcome Variable:** The secondary outcome variable for this study will be change in blood pressure, glucose, and weight.

c. Statistical plan including sample size justification and interim data analysis.

The trial has sufficient resources and adequate power to enroll 150 participants, who will be randomly allocated in equal proportions to the 2 groups: **Group A:** Self-Shopping DASH (S-DASH) diet advice group. **Group B:** Coaching DASH (C-DASH) diet advice group. The primary contrast is the difference in the percent change in (B vs. A) in urine albumin excretion (Urine Albumin to creatinine ratio, mg/g: UAlb/Cr mg/g). We used the standard deviation of the percent difference in the Urine Alb/Cr (post-pre/pre) of 63% and 53% in the intervention arm and the control arm, respectively. These variance estimates are from our pilot study (Five, Plus Nuts and Beans) published in 2016. The pilot trial enrolled African American patients with hypertension (similar to our eligibility criteria). Although albuminuria was not an eligibility criterion, 17 of 123 randomized had albuminuria (UAlb/CR ≥30 mg/g).

Principal Investigator: [name], ScM

Application Number: IRB00122943

Power calculations for our trial are based on a basic model that compares (4 month - baseline) differences among treatment groups (**Table**). The trial has 80% power to detect a treatment effect of 20% difference between arms at  $\alpha = 0.05$  if we enroll 150 participants. For this estimate, we set the correlation between

baseline and follow-up at 80%. This is a conservative estimate as the correlations of the log Alb/Cr between pre and post measurements in the pilot trial was 0.92 and 0.82 in the intervention and the control group, respectively. The weaker correlation in the intervention group would be expected, as variability in response to treatment in this arm would be greater. These treatment effects are achievable. In the pilot trial, the effect size noted was a ~39% difference (N=17) between the 2 arms in the subgroup with UAlb/Cr ≥30 mg/g at baseline. In the ACT Trial (a second trial of blood pressure management strategies in African Americans with uncontrolled

Net treatment	Power for	Sample
effect, % difference	single test	size
in UAlb/Cr	at $\alpha$ =0.05	needed
20%*	0.8	148

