25%*	0.8	96
20% **	0.8	152

\*SD of %change is 63% and 53% in intervention and control arm, respectively (from 5+plus study).

hypertension) we observed a 31% difference between arms in the subgroup of participants with UAlb/Cr  $\geq$ 30 mg/g (N=34). Hence, our goal of achieving a 20% contrast is likely. As a secondary source of variance data we used SD of change data and sample size estimates published in 2016 (Sontrop JM et al., 2016) derived from a population of adults with CKD and based on a SD of change of 49% (less than what we observed) . In that study they report that the sample size needed to detect a 20% difference in UAlb/Cr would be N=152 (correlation was not reported). Secondary analyses of effects on blood pressure and weight will be evaluated at the nominal  $\alpha = 0.05$  level. This trial is not powered to see an effect on these secondary outcomes, yet analyses of effect of the intervention on protocol driven BP and weight measurements will be assessed.

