# **Analysis Plan**

This trial is a randomized trial that tests the effects of an innovative intervention against a minimal intervention on a selected set of outcomes. The primary contrast is (A vs. B) in Urine albumin excretion (**Primary Specific Aims**). For secondary analyses, we will test the contrast for reducing blood pressure, glucose, and weight (**Secondary Aim**). The analysis will be conducted under the intent-to-treat principle for both the Primary and the Secondary Aims before any supplemental analyses are conducted.

For the **Primary Aim**, groups will be compared using within-person differences in outcome levels obtained on those diets. Because we anticipate some dropouts (although there were none in the pilot), we will conduct our primary analysis using mixed effects modeling (likelihood) and multiple imputation approach under the missing at random (MAR) assumption. We will adjust for baseline UAlb/Cr which should increase our power and account for any power lost by drop-outs. We will then carefully examine all available data and build sensitivity analyses using clinically sensible missing scenarios to evaluate the potential impact by non-ignorable missing data. A parallel approach will be used for **Secondary Outcomes.** Distribution of data will be checked and transformed where appropriate. Other outcome variables will be analyzed with a similar approach. Adjustments for baseline variables will be made, where appropriate, in multivariable analyses. Ninety-five percent confidence intervals of the estimated mean differences will be constructed for each outcome.

\*\*SD of change of 49% (Sontrop JM et al., 2016

Principal Investigator: [name], ScM

Application Number: IRB00122943

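### The stated 80% power for a 20% difference with 150 participants does not follow from the plan's own SDs of percent change, which give about 56%, or about 60% with baseline adjustment

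*Combined protocol and SAP*

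**What the plan says.** All the inputs are in section 7c, apart from the analysis model, which is under Analysis Plan.

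- **Claim.** "The trial has 80% power to detect a treatment effect of 20% difference between arms" at alpha 0.05 with 150 participants, allocated equally. The table gives 148 for a 20% net effect and 96 for 25%, both at power 0.8.
- **Variance.** "We used the standard deviation of the percent difference in the Urine Alb/Cr (post-pre/pre) of 63% and 53% in the intervention arm"; the second figure belongs to the controls, and both come from the pilot. The footnote to the two rows repeats this: "SD of %change is 63% and 53% in intervention and control arm, respectively (from 5+plus study").
- **Model.** "Power calculations for our trial are based on a basic model that compares (4 month - baseline) differences among treatment groups".
- **Correlation.** The value between "baseline and follow-up at 80" per cent is called conservative, against pilot values of 0.92 and 0.82 for log albumin-to-creatinine ratio.
- **Third table row.** This is 152 participants for 20%, "based on a SD of change of 49% (less than what we observed"). It is attributed to a published study in adults with CKD: "In that study they report that the sample size needed to detect a 20% difference in UAlb/Cr would be N=152".
- **Analysis.** "We will adjust for baseline UAlb/Cr which should increase our power and account for any power lost by drop-outs".

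The section does not state sidedness, a formula, a drop-out rate, or any averaging of repeated samples for the power calculation.

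**The concern.** The table shows the problem before any calculation. For the same 20% effect and the same power, SDs of 63% and 53% are said to need fewer participants (148) than an SD of 49% (152), although the text itself calls 49% the smaller figure. The two figures come from different sources and may be on different scales. Even so, 148 looks too small for the SDs beside it.

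This table is the only support for the statement that the trial has adequate power for its primary outcome. If power for the 20% target is nearer 56% than 80%, a true effect of that size would be missed about 44% of the time rather than 20%. A reader relying on the stated 80% would read too much into a non-significant result.

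**Working it through.** **Inputs.** SDs of percent change 0.63 and 0.53; 75 per arm; alpha 0.05; differences d = 0.20 and 0.25 (all section 7c). Two-sided testing is assumed, which the 95% confidence intervals in the Analysis Plan support.

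**Sample size under the stated model**

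- Sum of variances: 0.63² + 0.53² = 0.6778. The root mean square SD is √(0.6778/2) = 0.582.
- n per arm = (1.960 + 0.842)² × 0.6778 / d² = 7.849 × 0.6778 / d².
- d = 0.20: 133.0 per arm, **266** in total (stated 148).
- d = 0.25: 85.1, rounded up to 86 per arm, **172** in total (stated 96).

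**Power at the planned size**

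- 75 per arm, d = 0.20: Φ(0.20/√(0.6778/75) − 1.960) = Φ(2.104 − 1.960) = **0.557** (0.552 by noncentral t).
- At the table's own sizes: 74 per arm and d = 0.20 give 0.552; 48 per arm and d = 0.25 give 0.557. Both rows miss by the same amount, so this is not rounding.
- Difference detectable with 80% power at 75 per arm: √(7.849 × 0.6778/75) = 0.266, about 27 points.
- Common SD of change at which 150 participants would give 80%: √(0.04 × 75/(2 × 7.849)) = 0.437, against 0.582 as stated.

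**What the correlation can add.** An SD of change already reflects the pre/post correlation r. Adjusting a change score for baseline multiplies its variance by (1 − r²)/(2(1 − r)) = (1 + r)/2. This assumes a difference with equal pre and post variances. The outcome here is a ratio to baseline, so the adjusted figures are approximate.

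- r = 0.8, factor 0.90: 240 and 154 participants, power **0.602**, detectable difference 25.3 points.
- r = 0.82: power 0.597. r = 0.92: power 0.574.

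**Other readings of the same inputs** (75 per arm, 20% effect)

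| Reading | Power | Power, baseline-adjusted (r = 0.8) |
|---|---|---|
| One-sided 0.05 | 0.677 | 0.717 |
| SDs used directly as log SDs, effect ln(0.8) = −0.223 | 0.651 | 0.696 |
| SDs converted to log scale by √ln(1 + CV²) | 0.717 | 0.761 |

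Reading 63% and 53% as single-visit SDs gives 108 participants by change score or 96 by ANCOVA for the 20% row. That is not 148, and it contradicts the footnote.

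**Reproducing 148 and 96.** Two routes give both entries exactly:

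- Dividing the per-arm n by 1 + r: 133.0/1.8 = 73.9 and 85.1/1.8 = 47.3, rounded up and doubled.
- Inflating the per-arm n for 10% loss and reading the result as a total: 133/0.9 = 147.8 and 86/0.9 = 95.6, rounded up.

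The first is not a standard formula and uses the correlation twice. The second mistakes a per-arm size for a total. The documents describe neither, so the cause is unknown.

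**The 152 row.** With SD 0.49, two-sided: d = 0.20 gives 94.2 per arm (190 in total), and |ln 0.8| = 0.223 gives 75.7 per arm (152). The row fits a log-scale calculation, so it may not be comparable with rows 1 and 2.

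**Drop-out** (rates assumed; none is given). With adjustment at r = 0.8, 10% loss leaves 67.5 per arm and power 0.557. At 20% loss, 60 per arm gives 0.509.

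**The case against.** The strongest counter-argument is repeated sampling. Table 1 schedules urine at both screening visits and two samples at month 4, and the Analysis Plan uses mixed models. If the pilot SDs describe single samples and every pairwise correlation is 0.8, averaging two baseline and two follow-up samples halves the change variance. That gives 134 participants and 84.5% power at 150. One baseline with two follow-up samples gives 68%, or 74% adjusted. One baseline with the mean of three follow-up samples, adjusted, gives 152 and 98 participants, close to the table. Adequate power therefore cannot be ruled out. But the plan states none of these assumptions, and its stated model is a simple 4-month-minus-baseline comparison. What stands is that 56% and 60% should be labelled as the result for the stated inputs, without averaging.

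Second, the other variance source is more favourable: SD 49% on the log scale gives 79.6% power at 150, in a CKD population. Only 17 of the 123 pilot participants had albuminuria, so the pilot SDs may not fit this trial's population. That would be a reason to choose the other SD openly. It does not make rows 1 and 2 follow from 63% and 53%.

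Third, the plan cites larger subgroup differences of 31% and 39%, for which the stated SDs give about 90% and 98% power. Those estimates rest on 34 and 17 participants, and the claim under review concerns 20%.

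Finally, a non-significant result is read mainly through its confidence interval, which is planned. That is true, but the power statement is still wrong as written.

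**Conclusion.** The concern holds. On the SDs and model that the plan states, 150 participants give about 56% power for a 20-point difference, or about 60% with baseline adjustment, and rows 1 and 2 should read 266 and 172 (about 240 and 154 adjusted). This rests on two-sided alpha 0.05, the SDs meaning what the footnote says, no averaging of samples and no drop-out. One-sided and log-scale readings raise power to between 65% and 76%, still short of 80%. Averaging could close the gap only under assumptions absent from the plan. The ordering of 148 and 152 is a warning sign rather than proof of contradiction, because the 152 may be on another scale.

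**What to change.** 1. Restate the power sentence and the first two table rows, with the formula, scale, sidedness and use of the correlation. For example: *With SDs of percent change of 63% and 53%, 75 per arm and two-sided alpha 0.05, a comparison of single-sample change scores has about 56% power for a 20-point difference (about 60%, approximately, after baseline adjustment at r = 0.8). The difference detectable with 80% power is about 27 points (about 25 adjusted). 80% power for 20 and 25 points would need 266 and 172 participants (about 240 and 154 adjusted).* If another formula or scale was used, or if averaging of urine samples was relied on, show it with SDs and correlations on that basis.
2. Label the scale of the 49% row, or stop using it as corroboration.
3. In the Analysis Plan, qualify the claim that baseline adjustment makes up for drop-out: at r = 0.8 it offsets about 10% loss, and only back to about 56% power.

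The cost is wording in the sample-size section and table, plus one qualifier. The stated power becomes less favourable; enrolment, visits and analysis do not change.

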# **Analysis Plan**

This trial is a randomized trial that tests the effects of an innovative intervention against a minimal intervention on a selected set of outcomes. The primary contrast is (A vs. B) in Urine albumin excretion (**Primary Specific Aims**). For secondary analyses, we will test the contrast for reducing blood pressure, glucose, and weight (**Secondary Aim**). The analysis will be conducted under the intent-to-treat principle for both the Primary and the Secondary Aims before any supplemental analyses are conducted.

For the **Primary Aim**, groups will be compared using within-person differences in outcome levels obtained on those diets. Because we anticipate some dropouts (although there were none in the pilot), we will conduct our primary analysis using mixed effects modeling (likelihood) and multiple imputation approach under the missing at random (MAR) assumption. We will adjust for baseline UAlb/Cr which should increase our power and account for any power lost by drop-outs. We will then carefully examine all available data and build sensitivity analyses using clinically sensible missing scenarios to evaluate the potential impact by non-ignorable missing data. A parallel approach will be used for **Secondary Outcomes.** Distribution of data will be checked and transformed where appropriate. Other outcome variables will be analyzed with a similar approach. Adjustments for baseline variables will be made, where appropriate, in multivariable analyses. Ninety-five percent confidence intervals of the estimated mean differences will be constructed for each outcome.

\*\*SD of change of 49% (Sontrop JM et al., 2016

Principal Investigator: [name], ScM

Application Number: IRB00122943

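### Baseline adjustment cannot make good any power lost to drop-out: taking the plan's 148 at face value with r = 0.80 it offsets at most about 11% loss, and with the SDs as labelled none

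*Combined protocol and SAP*

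**What the plan says.** Section 7.c (Study Statistics) bases power on a change score: "Power calculations for our trial are based on a basic model that compares (4 month - baseline) differences among treatment groups". The stated result is "The trial has 80% power to detect a treatment effect of 20% difference between arms at" a significance level of 0.05 with 150 enrolled. The variance input is the "standard deviation of the percent difference in the Urine Alb/Cr (post-pre/pre) of 63% and 53% in the intervention arm and the control arm", taken from the pilot. The correlation is set between "baseline and follow-up at 80" percent.

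The sample size table gives 148 for a 20% difference and 96 for 25%, both on the pilot SDs. It gives 152 for 20% on an SD of change of 49% from a published CKD study: "In that study they report that the sample size needed to detect a 20% difference in UAlb/Cr would be N=152". Section 7 contains no drop-out rate and no inflation for loss.

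The Analysis Plan, in the same section, expects some drop-outs, notes that the pilot had none, and specifies mixed-effects modelling and multiple imputation under MAR. On power it says: "We will adjust for baseline UAlb/Cr which should increase our power and account for any power lost by drop-outs".

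**The concern.** The sentence sets no limit on the loss that adjustment is said to cover. Yet the baseline value is already used in the power calculation, because the outcome there is change from baseline with a stated correlation. Going from a change score to a baseline-adjusted comparison brings only a further, modest gain.

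The sample size has almost no slack of its own: 150 against 148 is a margin of 2 participants (1.3%), and 150 is below 152. The retention evidence cited is full follow-up in an 8-week pilot, whereas the powered contrast here is at 4 months. Section 4 also provides for premature removal of participants who develop an exclusion criterion. A reader of the plan would take 80% power as secure whatever the retention.

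**Working it through.** **Inputs.** Difference 20 percentage points, power 80%, 1:1 allocation, SDs 63% and 53%, r = 0.80, N needed 148 or 152, enrolment 150 (all Section 7.c). Sidedness is not stated. Two-sided alpha of 0.05 is assumed, in line with "Ninety-five percent confidence intervals of the estimated mean differences will be constructed for each outcome". Then z = 1.960 + 0.842 = 2.8016 and z² = 7.849. Normal approximation throughout.

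**1. The plan's own figure.** With the SDs used as labelled (SD of percent change):

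- n per arm = (63² + 53²) × 7.849 / 20² = 6778 × 7.849 / 400 = 133.0, so N = 266, not 148.
- Other readings for 20%: one-sided 210; log scale with ln(0.8) 214; labelled SDs with the adjustment factor 0.90, 240; SDs treated as single-visit SDs, 108 with the change-score factor 2(1−r) = 0.40, or 96 with the adjusted factor 1−r² = 0.36.
- Dividing 133.0 by 1+r = 1.8 gives 73.9, i.e. 74 per arm and 148. The same division gives 96 for a 25% difference. But 1/(1+r) is not a standard variance factor for either a change-score or a baseline-adjusted comparison.
- The 152 row does reproduce: 2 × 0.49² × 7.849 / ln(0.8)² = 75.7, i.e. 76 per arm, with no correlation and no drop-out.

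**2. What adjustment adds, taking 148 at face value as a change-score N at r = 0.80.** With equal baseline and follow-up variances,

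Var(adjusted) / Var(change) = (1−r²) / [2(1−r)] = (1+r)/2 = 0.90.

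- Completers needed: 148 × 0.90 = 133.2. Tolerable loss from 150: 1 − 133.2/150 = 11.2%, or 10.7% after rounding up to 134. This includes the 2 spare participants; adjustment alone gives 10%.
- On the 152 row, with the same factor assumed: 152 × 0.90 = 136.8, and 1 − 136.8/150 = 8.8%.

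**3. Power for 150 enrolled at assumed losses d.** Power = Φ(2.8016 × √[150(1−d) / (148f)] − 1.96), with f = 1 unadjusted and f = 0.90 adjusted. The documents give no drop-out rate, so every d is an assumption.

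| Loss of month-4 ACR | 0% | 10% | 15% | 20% | 30% |
|---|---|---|---|---|---|
| Unadjusted change score | 80.5% | 76.3% | 73.9% | 71.3% | 65.5% |
| Baseline-adjusted, r = 0.80 | 84.4% | 80.5% | 78.3% | 75.8% | 70.1% |

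**4. The same question with the SDs as labelled.** At 75 per arm with no loss:

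- Unadjusted: 20 / √(6778/75) = 2.104; power = Φ(2.104 − 1.960) = 55.7%.
- Adjusted at r = 0.80: 20 / √(0.90 × 6778/75) = 2.218; power = Φ(0.258) = 60.2%.

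Power is below 80% before anyone is lost, so measured against the stated 80% adjustment offsets no drop-out.

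**The case against.** **The tolerance rests on 148, which does not reproduce.** This stands, and it is why the 11% is conditional. If 148 already reflects baseline adjustment, there is no further gain and only the 2 spare participants (1.3%) remain. If 63% and 53% were really single-visit SDs, N would be 108 or 96 and 150 would leave 28 to 36% for loss. Section 7.c and the table footnote label them as SDs of percent change, so that reading goes against the text. No reading supports an unlimited claim.

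**A reader might infer that the pilot correlations of 0.82 and 0.92 make the cushion smaller still, because (1+r)/2 approaches 1 as r rises.** The documents do not support that. If 148 is a change-score N that depends on r, its variance scales as 2(1−r), so a higher r would also lower the 148. Holding 148 fixed while changing r mixes two incompatible assumptions. Only the figure at the plan's own r = 0.80 is used here.

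**A reader might infer that baseline adjustment is the plan's only protection against missing data.** It is not. The same paragraph plans likelihood-based mixed models, multiple imputation and sensitivity analyses for non-ignorable missingness. ACR is also measured at month 1, so these methods may recover some information when month 4 is missing. The second urine sample around month 4 may add precision as well. The plan quantifies none of this.

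**The loss rates are hypothetical.** True. The powered contrast is at month 4, while the food allowance is still running, so 12-month attrition is not the relevant exposure. Whether a cushion of about 11% is enough depends on a rate that the plan does not state.

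**Conclusion.** The claim that baseline adjustment accounts for any power lost to drop-out is not correct. Accepting 148 as a change-score N at r = 0.80, with equal baseline and follow-up variances, adjustment and the 2 spare participants together offset at most about 11% loss of month-4 ACR (about 9% on the 152 row). Beyond that, power falls below 80%: about 76% at 20% loss and 70% at 30%.

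This is a favourable case. With the SDs used as labelled, about 266 participants are needed. Power at 150 is then about 56% unadjusted or 60% adjusted with full retention, and nothing is left to absorb loss. The unexplained 148 therefore matters more than the attrition wording and has to be settled first.

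It would go too far to conclude that drop-out will in fact make the trial miss 80% power, or that there is no cushion on any reading. The stated calculation contains no attrition allowance, but the adjusted analysis supplies a limited one if 148 is right, and the documents give no expected drop-out rate.

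**What to change.** 1. In the Analysis Plan, delete the second half of the sentence, which says that adjustment accounts for power lost to drop-outs. The statement that adjustment should increase power can stay.
2. In Section 7.c, state the SD, the outcome scale (percent change or log ratio), the sidedness, the use made of r and the formula that together give 148 and 96. If they do not reproduce, correct the stated power for 150.
3. Then add to the table the power for 150 enrolled under the baseline-adjusted analysis, with 0, 10, 15, 20 and 30% of month-4 ACR missing, marked as assumed rates. If step 2 confirms 148 as a change-score N at r = 0.80, the adjusted row under working supplies these values. If not, recompute them; they should not be anchored to an unexplained 148.

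The cost is a deleted clause, a short derivation and one table line. Enrolment stays at 150. The downside is a less favourable stated power.
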